2. INTRODUCTION

Study KAN-101-02 is a 3-part, multicenter Phase 1b/2 study of KAN-101 in participants with celiac disease (CeD) on gluten-free diet (GFD). The 3 parts include: Part A – Open-label, multiple ascending dose (MAD); Part B – Double-blind, placebo (PBO)-controlled, parallel design (participants have baseline gluten change at Day -21); Part C – Double-blind, PBO-controlled, parallel design (there is no baseline gluten change).

This SAP provides the detailed methodology for summary and statistical analyses of the data collected in study KAN-101-02 Part C. As the populations for Part B and Part C are different (Part B participants have to demonstrate a symptomatic response following a 1-day oral GC performed during Run-in. There is no such requirement for Part C). Part B and Part C data will not be combined for analysis. This document may modify the plans outlined in the protocol; however, any major modifications of the primary endpoint definition or its analysis will also be reflected in a protocol amendment.

2.1. Modifications to the Analysis Plan Described in the Protocol

“Entered” analysis set is added to [Section 4](#), it is not in the protocol. The definition of “Enrolled” analysis set is different from that in the protocol.

2.2. Study Objectives, Endpoints, and Estimands

Study Part C objectives, corresponding endpoints, and estimands are provided in the Table 2 below.

Table 2. Objectives, Endpoints, and Estimands

Objectives	Endpoints	Estimands
Primary:		

 Compare change in biomarker (IL-2) response following GC in participants with CeD treated with KAN-101 versus PBO. 	
 Change in levels of IL-2 from pre-GC to post-GC on Day 15. 	
 Estimand 2: a hypothetical estimand;
Secondary:		

 Assess the pharmacokinetics (PK) of multiple doses of KAN-101 in participants with CeD. Assess the safety and tolerability of KAN-101 in participants with CeD. 	
 KAN-101 plasma exposure as data permit: AUC_{inf}, AUC_{last}, C_{max}, T_{max} and t_{1/2}. Incidence and severity of treatment-emergent adverse events (TEAEs) as assessed by the Common Terminology Criteria for Adverse Events (CTCAE). 	
 N/A.

Table 2. Objectives, Endpoints, and Estimands

Objectives	Endpoints	Estimands
Tertiary/Exploratory:		

 • To further characterize the PK profile of KAN-101 following multiple doses in participants with CeD. • To evaluate the immunogenicity of KAN-101. • Assess the incidence of CeD symptoms in participants with CeD. • Compare change in biomarker response in participants with CeD and treated with KAN-101 versus PBO. • Assess durability of biomarker (IL-2) response in peripheral blood of participants with CeD and treated with KAN-101 versus PBO. 
Biopsy Substudy:
 
 • To evaluate the impact of KAN-101 on histology from esophagoduodenoscopy (EGD) biopsy in participants with CeD. • Evaluate the potential relationship between histopathological state and response to 1 day GC 	
 • KAN-101 PK parameters, as data permit: AUCinf (dn), AUClast (dn), Cmax(dn), CL, V. • Incidence of development of anti-drug antibodies (ADA) during the study. • Incidence of CeD symptoms as assessed by Patient Reported Outcomes (PROs) including: celiac disease symptom diary (CDSD) v2.1, patient global impression of change (PGIC) and patient global impression of severity (PGIS). • Change in circulating levels of IL-2 from pre-GC to and post-GC at Weeks 12, 24, and 36. • Change in circulating levels of various biomarkers from pre-dose to post-dose on Day 1, 4, and 7 (This analysis will be performed separately, not be included in the CSR). • Change in circulating levels of IL-2 pre- and post-GC in peripheral blood from Day 15 to Weeks 12, 24, and 36. 
Biopsy Substudy:
 
 • Change from baseline in histology (including, but not limited to, Marsh score, villous height crypt depth ratio, IEL counts) at Week 52. • Correlation between histological state, symptomatic response and biomarker responses (IL-2). (This analysis will be performed separately, not be included in the CSR) 	
 • N/A.

2.2.1. Primary Estimand

Estimand 2: The primary estimand is hypothetical, which estimates the treatment effect of KAN-101 vs PBO for IL-2 under the scenario of no intercurrent events. It includes the following 5 attributes:

- Population: Participant with CeD as defined by the Part C inclusion and exclusion criteria.
- Variable: log transformed IL-2 change from pre-GC to post-GC at Day 15.
- Treatment conditions: 3 dose groups of KAN-101 or PBO.
- Intercurrent Events: Prohibited medication, incomplete GC on Day 15, and discontinuation of study intervention. All data collected after any intercurrent events will be excluded.
- Population level summary: The LSM difference of the change from pre-GC to post-GC (log transformed) between each KAN-101 group and PBO.

2.2.2. Secondary Estimand

Estimand 3: This is a treatment policy estimand, which estimates the treatment effect of KAN-101 compared with PBO without regard to intercurrent events. It includes the following 5 attributes:

- Population: Participant with celiac disease as defined by the Part C inclusion and exclusion criteria.
- Variable: log transformed IL-2 change from pre-GC to post-GC at Day 15.
- Treatment condition: 3 dose groups of KAN-101 or PBO;
- Intercurrent event: intercurrent events will not be considered for analysis.
- Population-level summary: the LSM difference of the change from pre-GC to post-GC (log transformed) between each KAN-101 group vs PBO.

Estimand 3 will be used as a sensitivity analysis for the primary endpoint in Part C.

2.3. Study Design

Study KAN-101-02 is a 3-part, multicenter Phase 1b/2 study of KAN-101 in participants with CeD on GFD. The 3 parts include:

- **Part A** – Open-label, multiple ascending dose
- **Part B** – Double-blind, PBO-controlled, parallel design

DMB02-GSOP-RF02 7.0 *Statistical Analysis Plan Template* 31-Jan-2022

PFIZER CONFIDENTIAL

TMF Doc ID: 98.03

Page 10 of 30

- **Part C** – Double-blind, PBO-controlled, parallel design

Part C is a Phase 2, double-blind, PBO-controlled, parallel design study to compare the biomarker response (plasma IL-2; primary endpoint) following GC on Day 15. Safety, tolerability, and PK of KAN-101 in adult participants (18 to 70 years inclusive) with histology-confirmed CeD will also be evaluated.

[figure not shown]
Eligible participants will be randomized 1:1:1:1 and stratified by participation in biopsy substudy to one of the following 4 treatment groups and administered study intervention IV for 3 administrations (1 administration every 3 days starting at Day 1):

- PBO (Group 1)
- 0.6 mg/kg (Group 2)
- 1.2 mg/kg (Group 3)
- 3.0 mg/kg (Group 4)

All participants will return to the clinic at Day 15, Weeks 12, 24, and 36 to receive a 1-day 9 g oral GC to assess plasma IL-2 biomarker response to gluten and collect symptom information and follow-up visits on Day 28 and Week 52.

Participants participating biopsy substudy at applicable sites will receive biopsies at screening and Week 52.

Figure 1. Part C Study Design Schema

† Biopsy only collected as part of Biopsy Substudy at applicable sites.

3. ENDPOINTS AND BASELINE VARIABLES: DEFINITIONS AND CONVENTIONS

3.1. Primary Endpoint

- Change in IL-2 from pre-GC to post-GC on Day 15 (log transformed IL-2 values will be used in analysis model).

3.2. Secondary Endpoints

- KAN-101 plasma exposure as data permit: AUC_{inf} , AUC_{last} , C_{max} , T_{max} and $t_{1/2}$.

Parameter	Definition	Method of Determination
AUC_{last}	Area under the plasma concentration-time profile from time 0 to the time of the last quantifiable concentration (C _{last})	Linear/Log trapezoidal method
AUC_{inf}	Area under the plasma concentration-time profile from time 0 extrapolated to infinite time	$AUC_{last} + (C_{last}/K_{el})$, where C _{last} is the predicted plasma concentration at the last quantifiable time point estimated from the log-linear regression analysis

Parameter	Definition	Method of Determination
C_{max}	Maximum plasma concentration	Observed directly from data
T_{max}	Time to first occurrence of C_{max}	
$t_{1/2}$ ^a	Terminal elimination half-life	$\text{Log}_e(2)/K_{el}$, where K_{el} is the terminal Phase rate constant calculated by a linear regression of the loglinear - concentration time- curve. Only those data points judged to describe the terminal log-linear decline will be used in the regression

a. If data permits.

- Incidence and severity of TEAEs as assessed by the CTCAE.

See [Section 3.5.1](#).

3.3. Exploratory Endpoints

- KAN-101 PK parameters, as data permit: $AUC_{last}(dn)$, $AUC_{inf}(dn)$, $C_{max}(dn)$, CL, V.

Parameter	Definition	Method of Determination
$AUC_{last}(dn)$	Dose normalized AUC_{last}	AUC_{last}/Dose
$AUC_{inf}(dn)$	Dose normalized AUC_{inf}	AUC_{inf}/Dose
$C_{max}(dn)$	Dose normalized C_{max}	C_{max}/Dose
CL ^a	Apparent systemic clearance	Dose/AUC_{last}
V ^a	Apparent volume of distribution following IV dosing	$\text{Dose}/AUC_{inf} \times K_{el}$

a. If data permits.

- Incidence of development of ADA during the study

Positive of ADA will be assessed at Days 1, 7, 28, Weeks 12, 24, 36, 52 or early termination (ET) visit.

- The observed value and the change in CSDS

CSDS is a patient reported outcome (PRO) questionnaire. The version 2.1 includes 5 severity items and 3 frequency supplement questions (see [Appendix 2.2](#)) that will be collected daily. Each individual item and question as well as the CSDS Total Score (calculation found in [Appendix 2.2](#)), CSDS GI Score will be summarized and analyzed for weekly average at weeks 3, 12, 24, 36, as well as for daily assessment at GC Day 15, and Weeks 12, 24, 36 GC. Baseline CSDS is the average of most recent 7-day interval scores before Day 1 (not include Day 1) with at least 4 days with non-missing scores. If there are ≥ 4 days missing scores within any 7-day interval before Day 1, the baseline is set as missing. The weekly average score is the weekly sum score divided by the number of days with non-missing in that week. If daily scores are missing for more than half of total days in a specific week, the average score is missing for that week. Weeks 3, 12, 24, 36 average will be calculated. The start day for each week is the GC day at the related time point (see [Table 7](#)).

Change from baseline at each timepoint = observed value (or derived as above) at each timepoint – baseline.

- The change from baseline in CSDS Nausea score and vomiting frequency for Day 15, Week 12, Week 24 and Week 36 will be calculated as a 1 day, 3-day average, and 7-day average (weekly average) score. The start day for 1-day, weekly and 3-day interval is the GC day at the related time point (see [Table 7](#)). If daily scores are missing for more than half of total days in a specific week or the score on GC day is missing, the average score is set as missing for that week. If ≥ 2 observations are missing for a 3-day interval, the 3-day average score will not be calculated. If the score is missing on the GC day, the 3-day and 7-day average at that time point are set as missing as well. The baseline as described in previous paragraph will be used as the baseline to calculate the change from the 1-day, 3-day and 7-day score.
- The observed value and the change in PGIS

PGIS is a PRO questionnaire designed to assess the patient's impression of disease severity over the past week (see [Appendix 2.3](#)) that is collected at baseline (Day 1), Day 15, 28, Weeks 12, 24, 36, 52, or ET visit. Change from baseline at each timepoint = observed value at each timepoint – baseline. Baseline is the last non-missing value up to Day 1.

- The observed value in PGIC

PGIC is a PRO questionnaire designed to assess the patient's impression of the overall change in participant's celiac disease since receiving study intervention (see [Appendix 2.4](#)) that will be collected at Days 15, 28, Weeks 12, 24, 36, 52, or ET visit.

- The observed value and the change in IL-2 from pre-GC to post-GC at Weeks 12, 24, and 36 (log transformed IL-2 will be used in analysis model).
- The observed value and the change in circulating levels of IL-2 pre- and post-GC from Day 15 to Weeks 12, 24, and 36.

The change from Day 15 in circulating levels of IL-2 to Weeks 12, 24, or 36 is (post-GC IL-2 at each week – pre-GC IL-2 at each week) – (post-GC IL-2 at Day 15 – pre-GC IL-2 at Day 15). For analysis, log transformed IL-2 will be used.

- The observed value and the change from baseline in histology (including, but not limited to, Marsh score, villous height crypt depth ratio, IEL counts) at Week 52 for substudy.

3.4. Demographic and Baseline Variables

Demographic and baseline characteristics include:

- Age
- Sex
- Race
- Ethnicity
- Height (in cm)
- Weight (in kg)
- Body Mass Index
- Duration of CeD
- Duration of gluten-free diet (GFD)
- HLA genotype
- CeD Serology at diagnosis
- Histology at diagnosis
- PGIS
- CDS total score

3.5. Safety Endpoints

Safety will be assessed by medical history, vital signs, clinical laboratory tests, and the spontaneous reporting of AEs, in all participants who received any portion of study intervention. Unscheduled safety assessments may be performed at any time during the study to assess any perceived safety concerns. Investigators and Clinicians will review individual participant data throughout the conduct of the study to ensure participants' well-being. All the safety data will be summarized descriptively through appropriate data tabulations, descriptive statistics, and graphical presentations. All safety analyses will be performed on the safety population (See [Section 6.6](#)).

3.5.1. Adverse Events

Incidence and severity of TEAEs is the Secondary endpoint of Part C.

An adverse event (AE) is considered TEAE to a given treatment if the event start date is on or after the treatment period start date and before end of study.

The CTCAE (V5.0) displays Grades 1 through Grade 5 with unique clinical descriptions of severity for each AE based on below general guideline:

- **Grade 1:** Mild; asymptomatic or mild symptoms; clinical or diagnostic observations only; intervention not indicated.
- **Grade 2:** Moderate; minimal, local or noninvasive intervention indicated; limiting age appropriate instrumental activities of daily living (ADL).
- **Grade 3:** Severe or medically significant but not immediately life-threatening; hospitalization or prolongation of hospitalization indicated; disabling; limiting selfcare ADL.
- **Grade 4:** Life-threatening consequences; urgent intervention indicated.
- **Grade 5:** Death related to AE.

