 - **Run-in period:** 21 days; eligible participants will undergo 1-day 9g GC on first day of run-in period (at least 21 days before administration of first dose of study drug) to confirm symptomatic response to oral GC.
 - **Treatment period:** 7 days; symptomatic responders to the run-in GC will be randomized 1:1:1:1 to 1 of the 4 treatment groups and administered study intervention IV for 3 administrations (1 administration every 3 days starting at Day 1).
 - **Observation/follow-up period:** 358 days, including post-dosing GC on Day 15 (to assess primary endpoint), post-dosing GC at Weeks 12, 24 and 36 (to assess exploratory endpoints) and follow-up visits on Day 28 and Week 52.
- **Biopsy Substudy** (at applicable sites only, up to approximately 50% of Part B cohort): includes collection of duodenal biopsies at screening and Week 52.
- **Part C** – Part C is a Phase 2, double-blind, PBO-controlled, parallel design study to compare the biomarker response (plasma IL-2; primary endpoint) following GC on Day 15. Safety, tolerability, and PK of KAN-101 in adult participants (18 to 70 years inclusive) with histology-confirmed CeD will also be evaluated. Participants will be randomized 1:1:1:1 and stratified by participation in biopsy substudy to the following treatment groups:
 - PBO (Group 1)
 - 0.6 mg/kg (Group 2)
 - 1.2 mg/kg (Group 3)
 - 3.0 mg/kg (Group 4)
- Initiation of Part C will occur following the DSMB review of available safety data from Part B and the sponsor's approval.

- Part C will have 3 periods and 1 substudy:
 - **Screening period:** Day -28 to Day -1
 - **Treatment period:** Day 1 to Day 7; eligible participants will be randomized 1:1:1:1 to 1 of the 4 Treatment Groups and administered study intervention IV for 3 administrations (1 administration every 3 days starting at Day 1).
 - **Follow-up period:** Day after last dose till Day 364 (± 3 days), including post-dosing GC on Day 15 (to assess primary endpoint), post-dosing GC at Weeks 12, 24 and 36 (to assess exploratory endpoints) and safety follow-up visits on Day 28 and Week 52.
- **Biopsy Substudy** (at applicable sites only, up to approximately 50% of Part C cohort): includes collection of duodenal biopsies at screening and Week 52.

Number of Participants:

Part A: up to 12 participants will be randomized.

Part B: Approximately 16 participants (approximately 4 participants per treatment group) will be randomized.

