1.3.3. Part C (Phase 2 – Double-Blind)

Visit Identifier	Screen	Treatment Period				Follow-Up Period						ET	Notes
						GC	FU W4	GC W12	GC W24	GC W36	FU W52		
Abbreviations used in this table may be found in Appendix 13 .	Day -28 to Day-1	Day 1 (fasted)	Day 4 (fasted)	Day 7 (fasted)	Day 15 (fasted)	Day 28	Day 84 (fasted)	Day 168 (fasted)	Day 252 (fasted)	Day 364 (fasted)		
 Day relative to start of study intervention (Day 1). 	
Visit Window						±3 d	±5 d	±5 d	±5 d	±3 d		
 See Section 8.4.3 for follow-up AE and SAE assessments. 	
Screening Assessments													
Informed consent	X											
 Informed consent should be obtained prior to undergoing any study-specific procedures. See Section 10.1.3 for additional information. 	
Demographics and medical history	X											
 Includes disease history (symptoms at diagnosis and length of time on GFD). 	
Review eligibility criteria	X	X											
HIV, HBV, HCV testing	X												
HLA genotype and CeD serology	X											
 All participants will be assessed via central laboratory for HLA genotype and CeD serology (eg, tTG-IgA and DGP-IgG) at screening to confirm eligibility prior to screening GC. For rescreening: HLA does not need to be repeated and CeD serology only needs to be repeated if >3 months have elapsed from last assessment. 	
12-Lead ECG	X											
 Not required for participants who have had an ECG within 12 weeks prior to screening. 	
Clinical Procedures													
Physical examination	X									X	X	
 See Section 8.3.1 for additional information. 	
Vital signs	X	X	X	X	X	X	X	X	X	X	X	
 See Section 8.3.2 for additional information. Includes weight and height at screening only. 	
Orthostatic vital signs, oral temperature and RR		X	X	X								
 See Section 8.3.2.1 for additional information. To be measured pre-dose and at approximately 45 mins, 2 hours, and then, every 2 hours (until discharge) post end-of-infusion. Additional measurements may be taken in case of treatment-emergent, clinically significant orthostatic hypotension or syncope. See Section 8.3.2. 	
Contraception check	X	X	X	X	X	X					X		

090177e19fcc12ed\Approved\Approved On: 30-Jan-2024 19:45 (GMT)

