8.3.2. Vital Signs

Any untoward vital sign findings that are identified during the active collection period and meet the definition of an AE or SAE ([Appendix 3](#)) must be reported according to the processes in [Sections 8.4.1](#) to [8.4.3](#).

Vital signs will be monitored during and after study intervention infusions to assess for IRR (see [Appendix 9](#)). Vital signs will be taken before collection of laboratory tests. Height and weight will also be measured and recorded at screening only and captured on the CRF.

BP and PR assessment consists of a single measure of BP and a single PR. Sitting BP and PR measurement will be assessed with a completely automated device.

Manual techniques will be used only if an automated device is not available. BP and PR measurement should be preceded by at least 5 minutes of rest with the participant in a sitting position, in a quiet setting without distractions.

In amendment 3, Part C orthostatic vital signs including SBP, DBP, and PR will be collected as follows:

- Approximately 5 minutes pre-dose;
- Approximately 45 minutes, 2 hours, and then, every 2 hours until discharge, post dose.

Additionally, if a participant experiences treatment-emergent clinically significant orthostatic hypotension or syncope, then, in addition to supportive care, orthostatic vital signs including

DBP, SBP, and PR will be collected every 2 hours, until discharge. **Note:** if planned assessments (pre-dose and 45 min, 2 hr and 4 hour post-dose) overlap unplanned assessments, orthostatic vital signs will be measured only once, not twice at that time.

Measurement of orthostatic vital signs (SBP, DBP, and PR) will occur after:

1. participant has rested in supine position for 5 minutes
2. participant is in standing position for 1 min
3. Participant is in standing position for 3 minutes

Note: Clinically significant orthostatic hypotension (OH) is defined by a fall in systolic blood pressure over 20 mmHg or a fall of in diastolic pressure over 10 mm Hg within 3 minutes of standing. An increase in heart rate of over 30 bpm suggests postural tachycardia syndrome.(Freeman et al, 2011) In case of above, a Grade 3 AE will be documented.

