3. ENDPOINTS AND BASELINE VARIABLES: DEFINITIONS AND CONVENTIONS

3.1. Primary Endpoint

- Incidence and severity of TEAEs as assessed by CTCAE.

An adverse event (AE) is considered TEAE to a given treatment if the event start date is on or after the treatment period start date and before end of study.

The CTCAE (V5.0) displays Grades 1 through Grade 5 with unique clinical descriptions of severity for each AE based on below general guideline:

- **Grade 1:** Mild; asymptomatic or mild symptoms; clinical or diagnostic observations only; intervention not indicated.
- **Grade 2:** Moderate; minimal, local or noninvasive intervention indicated; limiting age appropriate instrumental activities of daily living (ADL).
- **Grade 3:** Severe or medically significant but not immediately life-threatening; hospitalization or prolongation of hospitalization indicated; disabling; limiting selfcare ADL.
- **Grade 4:** Life-threatening consequences; urgent intervention indicated.
- **Grade 5:** Death related to AE.

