6. ANALYSES AND SUMMARIES

6.1. Primary Endpoint

The primary endpoint for Part A is incidence and severity of TEAEs. Adverse events will be summarized for SAS according to Sponsor's reporting standards for

- TEAEs
- Serious AEs (SAEs)

TEAEs will be summarized overall and Day 1 to Day 15 prior GC by dose group by the number of participants reporting any TEAE, system organ class (SOC), preferred term (PT), severity, relationship to investigational product. CTCAE is used to grade the severity of AEs. TEAEs related to GC and infusion-related reactions (IRR) will also be summarized separately.

SAEs will be summarized by SOC and PT, and individual SAEs will be listed by participant.

A list of subjects who prematurely discontinue from the study due to an AE will be provided as well.

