3.5.3. Vital Signs

Vital signs will be assessed at Screening, Days 1, 4, 7, 15, 28, Weeks 12, 24, 36, 52, or ET visit. On dosing days, orthostatic vital signs including SBP, DBP, and PR will be collected approximately 5 minutes pre-dose, and approximately 45 minutes, 2 hours, and then, every 2 hours until discharge, post dose.

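### The TEAE rule uses the start date alone, so an AE that starts on Day 1 before the first infusion counts as treatment-emergent; in Part C this can be a Grade 3 orthostatic finding

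*SAP*

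**What the plan says.** **The TEAE rule.** In SAP Part C Section 3.5.1 an AE is "considered TEAE to a given treatment if the event start date is on or after the treatment period start date". SAP Part B Section 3.5.1 carries the same sentence. SAP Part A Section 3.1 has it too: the test is that the "event start date is on or after the treatment period start date and before end of study". None of the three names the infusion or a clock time.

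**The treatment period.** For Part C the Protocol synopsis gives "Day 1 to Day 7; eligible participants will be randomized". The schedule in Protocol Section 1.3.3 counts each "Day relative to start of study intervention (Day 1"), so Day 1 is the calendar day of the first infusion.

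**The pre-dose test.** In Part C, Protocol Section 8.3.2 places the first orthostatic reading at "Approximately 5 minutes pre-dose". SAP Part C Section 3.5.3 agrees for dosing days: "orthostatic vital signs including SBP, DBP, and PR will be collected approximately 5 minutes pre-dose". Section 8.3.2 calls orthostatic hypotension clinically significant when systolic pressure drops by more than 20 mmHg, or diastolic by more than 10 mmHg, in the first 3 minutes upright. It adds a heart-rate criterion and ends: "In case of above, a Grade 3 AE will be documented". The note is not restricted to post-dose readings.

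**Related rules.** AE collection starts at consent (Protocol Section 8.4.1). The vital-sign baseline window in SAP Part C Appendix 2.1, Table 4, runs through the first dosing date.

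**The concern.** A TEAE table is read as a record of what happened after exposure began. Under a date-only rule, anything that starts on the morning of Day 1 is included, even when it precedes the infusion. Often this is a harmless convention, because few AEs start in that gap. Part C is different: it puts a measurement in the gap that can itself generate an AE, at a grade fixed in advance.

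TEAE incidence and severity is a secondary endpoint of Part C. Protocol Section 4.2 says the added vital signs were meant to give insight into what follows dosing, and counting pre-dose readings as treatment-emergent works against that. Protocol Section 6.6.1.1 also sends Grade 3 or higher TEAEs to the DSMB. Finally, one reading can lie in the baseline window for vital signs and also be reported as a treatment-emergent Grade 3 event.

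**Working it through.** The plan states no figure on this point, so there is none to reproduce. The check has three steps.

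**1. Apply the rule as written.** Take four onset times and compare the date-only rule with a rule anchored on the date and time of the first infusion.

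| AE onset | Date-only rule | Date-and-time rule |
|---|---|---|
| Day -1 | not TEAE | not TEAE |
| Day 1, 5 minutes before infusion | **TEAE** | **not TEAE** |
| Day 1, 45 minutes after infusion | TEAE | TEAE |
| Day 4, before infusion | TEAE | TEAE |

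Only the Day 1 pre-dose onset changes. Pre-dose findings on Days 4 and 7 follow an earlier infusion and are correctly treatment-emergent under both rules.

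**2. Number of events.** The documents give no rate p of qualifying falls at the Day 1 pre-dose test, so p is assumed. The Protocol synopsis gives about 26 participants per group and 104 in total. Expected events = n × p. The chance of at least one in a group = 1 − (1 − p)^26.

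| Assumed p | Expected per 26 | Expected per 104 | Chance of at least one in a group |
|---|---|---|---|
| 1% | 26 × 0.01 = 0.26 | 1.04 | 1 − 0.99^26 = 23% |
| 2% | 0.52 | 2.08 | 41% |
| 5% | 1.3 | 5.2 | 74% |
| 10% | 2.6 | 10.4 | 94% |

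**3. Effect on a comparison of arms.** Assume, for illustration only, true post-dose rates of 10% on KAN-101 and 2% on placebo, with an independent 5% pre-dose rate in both.

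- KAN-101: 1 − (1 − 0.10)(1 − 0.05) = 14.5%.
- Placebo: 1 − (1 − 0.02)(1 − 0.05) = 6.9%.
- Risk difference: 14.5 − 6.9 = 7.6 points, against a true 10 − 2 = 8.0 points.
- Risk ratio: 14.5 / 6.9 = 2.1, against a true 10 / 2 = 5.0.

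The absolute contrast hardly moves. The ratio moves because a common background is added to a small placebo rate.

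**The case against.** The strongest reply is that the gap is narrow and partly covered.

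- **Start date.** The rule works on when an AE starts, not when it is found. An event noticed on Day 1 but recorded as starting earlier is not a TEAE. Someone who is not dosed after a pre-dose event is outside the safety analysis set. Both points stand, so the issue is confined to Day 1 pre-dose onsets in participants who then receive drug.
- **Grade 3 note.** Elsewhere in Protocol Section 8.3.2, and in 8.3.2.1 and 8.3.4, the orthostatic hypotension that triggers extra measurements is called treatment-emergent. One could read that limit into the Grade 3 note. But the note does not carry it, and the Protocol does not define the term.
- **Existing safeguards.** TEAEs are also tabulated by relationship to study drug, and a pre-dose event can be judged unrelated. That helps, but the all-causality and Grade 3 counts keep the event. SAP Part C Section 6.6.1 refers to the sponsor's reporting standards, which are not in the documents and cannot be shown to close the gap.
- **Inclusive by design.** A date-only rule errs towards counting more. That is reasonable when onset time is unknown, but less so when the event comes from a reading scheduled before the infusion.

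A reader might infer that worsening of an AE already open before dosing is lost. Protocol Section 10.3.1 makes an exacerbation an AE, so a worsening recorded that way has its own post-dose start date and is largely covered. A reader might also infer that Part C exists to study orthostatic hypotension. Protocol Section 4.2 shows otherwise: Part C was added without the screening gluten challenge, its primary objective is IL-2, and the orthostatic readings are supplementary.

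**Conclusion.** The point holds in a limited form and should be corrected. As written, the rule classes an AE that starts on Day 1 before any drug as treatment-emergent, and in Part C the schedule can produce such an AE at Grade 3. No other section removes it.

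The size rests on an unknown pre-dose rate: about 2 to 10 of 104 participants at an assumed 2% to 10%. A reader might infer a bias between arms, or a safety signal diluted by more than half, from the fall in risk ratio from 5.0 to 2.1. The documents do not support that. Pre-dose events should be balanced by randomisation, the rates are assumed, the risk difference barely changes, and TEAEs are summarised descriptively as counts and percentages with no ratio or test planned. The harm is inflated TEAE and Grade 3 counts.

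A reader might also infer that the Part A primary endpoint is seriously affected because it uses the same sentence. Parts A and B have no scheduled orthostatic test, so only incidental Day 1 events are exposed there. The main relevance is the Part C secondary safety endpoint.

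**What to change.** In SAP Part C Section 3.5.1, SAP Part B Section 3.5.1 and SAP Part A Section 3.1:

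- Define a TEAE as an AE that starts at or after the date and time of the start of the first infusion, keeping the existing upper limit.
- Count a Day 1 AE of unknown onset time as a TEAE unless the record shows onset before the infusion. The timed pre-dose orthostatic reading is one such record.
- List Day 1 pre-dose AEs separately, so that none disappears from the report.
- Optionally add that an AE present before the infusion and worsening after it is a TEAE, for consistency with Protocol Section 10.3.1.

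This fits distinctions the SAPs already make. SAP Part C Table 6 targets its immunogenicity baseline before dosing on Day 1, and SAP Part A Section 6.1 cuts within a day: "TEAEs will be summarized overall and Day 1 to Day 15 prior GC by dose group".

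The cost is SAP wording and a change to the TEAE derivation; no visit, procedure or grading rule changes. The small downside is that Day 1 onset times must be checked, because the documents do not show that AE onset time is collected. The default for unknown times is there for that reason.
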